Pentoxifylline Treatment in
Acute Pancreatitis: A Double-
Blind Placebo-Controlled
Randomized Trial

NCT 02487225

January 9, 2017

TITLE AND SUMMARY PAGE

Project Title: Pentoxifylline Treatment in Acute Pancreatitis; A Double-Blind Placebo-Controlled Randomized Trial

Principal Investigator:

[name] [name]
Section of Gastroenterology and Hepatology
Professor of Medicine
Mayo Clinic College of Medicine
[name]
[contact]
[contact]
[contact]

Participating Investigators:

[name].
[name].
[name]

Project Summary:

Background. Acute pancreatitis (AP) is a cause of significant morbidity and mortality and effective therapeutic regimens to treat this condition are lacking. Extensive experimental evidence indicates that tumor necrosis factor alpha (TNF- α) contributes to the pathogenesis of multiple organ failure (main cause of morbidity and mortality) in AP, suggesting a possible role for inhibition of TNF- α in the treatment of AP. There is no effective drug therapy for AP and hardly any human experience about the role of pentoxifylline in AP Methods: Randomized, double-blind, placebo-controlled study comparing three times daily dosing with Pentoxifylline from the time of admission until 72 hours of hospitalization in patients presenting with AP. Seventy-five patients will be enrolled in both the "treatment" and "placebo" groups (150 patients total). This study will be performed at Mayo Clinic, Rochester. Primary outcomes: Determine changes in CRP, TNF- α , IL-6, and IL-8 levels from admission baseline at one week.

Significance: If our hypothesis is confirmed this trial will be a landmark development in the treatment of AP. A simple, safe, and inexpensive drug that can be given to all patients with AP, in all settings, will be available to decrease the significant morbidity and mortality due to this disease.

PROJECT DESCRIPTION

Specific Aims:

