
Preliminary Results:

We have already successfully conducted a pilot double-blinded, placebo-controlled, allocation-blinded RCT of oral pentoxifylline in patients with AP with any one of several reported predictors of severe disease. By selecting many reported predictors of severity, we attempted to avoid as many patients with a mild form of the disease as possible. Both groups had 14 patients, evenly matched for age and sex; APACHE II and SIRS scores at admission; and pancreatic and/or peri-pancreatic necrosis. Compared to the placebo group, the pentoxifylline group experienced a 29% reduction in length of hospital stay, a 29% reduction in the need for an ICU stay, a 21% reduction in persistent organ failure, and a 7% reduction in pancreatic necrosis or fluid collection. The reductions translated to having no patients with: hospital stays over 10 days, an ICU need, persistent organ failure, interventions, or death in the pentoxifylline group . However, with the small sample size of this pilot study, these clinically significant differences failed to achieve statistical significance except for ICU need. There was no difference in the

inflammatory markers between the two groups over a short period of three days. We concluded that it is feasible to conduct a drug intervention study in a single institution, and pentoxifylline appeared safe and decreased the length of stay and the need for ICU intervention. With larger numbers, besides validating the above findings, we expect to see a beneficial

Experimental Design or Project Summary:

Acute pancreatitis (AP) is an inflammation of the pancreas gland and the most common gastrointestinal discharge diagnosis (approximately 280,000 admissions in 2009). It has resulted in \$2.6 billion, annually, in health care costs, mainly due to the more serious forms of the disease. Lack of any specific drug to treat the condition and predictors to identify patients who will develop more serious forms of the disease contribute to this. Long-term objectives of the study are to find a drug to treat this disease, improve patient outcomes, and reduce the costs of health care. Based on our experience with animals and a small, human subjects pilot study, our hypothesis and specific aims are:

1. Pentoxifylline, administered within 72 hours of diagnosis, improves the clinical outcomes and decreases the occurrence of more serious forms of AP.

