2. Pentoxifylline reduces the blood levels of inflammatory markers, which correlates with improvement in clinical outcomes. This study is a novel, exploratory clinical study of the effect of a drug that has a proven role in animal studies in blocking the inflammatory response in AP. It is also a high reward study that will lead to a breakthrough in the treatment of AP and challenge the age old recommendation of supportive treatment alone.

The study will have 2 groups of 75 patients each, all with AP, randomly assigned to either the drug or a placebo, which looks like the drug, for a period of 3 days or until the time they are discharged, if hospital discharge is within 7 days of admission. The levels of markers of inflammation (CRP, IL-6, IL-8 and TNF- α) will be measured at baseline and on 5 successive days or until the time of discharge, whichever occurs earlier. Determination of group size was based on the previous pilot study to decrease any of the important adverse outcomes, providing for a dropout rate of 10% during the study. During 2012, 263 patients with AP were admitted to this institution, which possesses the needed infrastructure for successful completion of clinical drug intervention trials. In the stipulated period of 2 years by the NIH, the required number of patients for the study could be recruited.

This project represents a single center study at Mayo Clinic Rochester. The trial is a randomized, double-blind, placebo-controlled study design.

Subjects: Subjects will be adult patients 18 years of age and greater which will be recruited from Mayo Clinic and admitted to the hospital with acute pancreatitis as defined by at least two of the following:

- amylase and/or lipase greater than 3 times the upper limit of normal values,
- characteristic cross-sectional imaging,
- characteristic pain syndrome.

If patients give consent to be in the study the PI may contact those patients before formally enrolling them in the study. By overseeing that one of the team (a study coordinator, PI, and co-investigator) is present during the weekends, we anticipate that those eligible patients during the weekend period are not going to be excluded.

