Randomization will be performed by the pharmacy under the direction of the study statistician, using randomized blocks, to ensure all clinical study personnel are blinded to patient allocation throughout the study. Subjects will be randomized into two groups. The "treatment group" will receive Pentoxifylline 400 mg one to three times daily by mouth from the time of enrollment until 72 hours from enrollment. Subjects will receive up to maximum of 9 doses of this medication. The "control" group will receive placebo dosing at similar intervals. Randomization will occur in a block fashion. Study medication will be administered at 1x/day if creatinine clearance \leq or \geq 30ml/min. per the manufacture prescribing information. All other treatment for AP (fluid resuscitation, antibiotics, surgical intervention, pain control, etc.) will be at the discretion of the primary care team. However, the study investigators will ask primary teams to follow standardized treatment guidelines for acute pancreatitis (to control for intravenous hydration and enteral nutrition, which may influence IL levels).

Blinding: Both subjects and investigators will be blinded to the randomization.

Sample Size:

We propose testing 75 patients in each study arm. Our primary outcome will be whether the patient develops any of the following outcomes of moderate or severe AP: hospital stay longer than 10 days, admittance to the ICU, persistent organ failure, pancreatic and/or peripancreatic necrosis and infection, SIRS, need for intervention, or death. In our pilot study, 7.1% of the patients on pentoxifylline experienced at least one of these outcomes, compared to 28.6% of those on the placebo. If extrapolated to the larger RCT, this reduction in events of these critical outcomes (7.1% vs. 28.6%) would represent a significant and meaningful difference for patients. Using a 5% 2-sided type I error, 58 patients in each group would be needed to achieve 80% power to detect the anticipated difference. In order to account for the unlikely event of up to 10% study dropout, we plan to enroll 64 patients in each group. We will use a randomized block design stratifying for predicted disease severity (mild, moderate, or severe).

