Data Collection and Handling: TNF- α , Il-6, and Il-8 will be handled by the research blood draw division of Mayo Clinic per usual practice. The C-RP testing on days 1, 3, 4 and 5 will be handled by the research blood draw division of Mayo Clinic per usual practice. The clinical and research laboratory data will be recorded every day until discharge. Early discharges before completion of 3 days of drug or 5 days of study of markers after drug administration is not considered as protocol violation and data until the time of discharge will be recorded for the purpose of analysis. Data Safety Monitoring Board (DSMB) will be constituted by clinicians having experience in TNF- α blockade therapy.

Data Analysis: All access to data will be password protected. Analysis will be on an-intent-to-treat basis. Outcomes will primarily be descriptive statistics such as means and percents. Continuous secondary end points will be analyzed with the t-test if the data are normally distributed and the Wilcoxon Rank Sum test if non-normal. Analyses of dichotomous secondary end points will use either the Chi-squared test or Fisher's Exact Test comparing proportions. Kaplan-Meier will be used to estimate survival. An interim analysis of data for preliminary review of less than target accrual may be done.

Feasibility: Nearly 250 patients with acute pancreatitis are seen at Mayo Clinic hospitals every year. Assuming ~60% of them are directly admitted to Mayo Clinic (not transferred from outside), and 50% agree to participate in the study it would take 24 months at Mayo to recruit 150 patients. If recruitment goals are not reached at Mayo Clinic after ~24months, the study may have to be extended for 6 months more. **Deliverables:**

We expect to publish at least one manuscript in a major academic journal as a result of this work. Our hope is that any reduction of morbidity or mortality from the novel therapy will have a profound effect on the treatment of acute pancreatitis and lead to future expanded clinical trials.

TAILED MILESTONES SCHEDULE

Endpoints:

May 2015 Mayo Institutional Review Boards (IRB) approval.

June 2015 Approximate NIH will release funds when IRB approved protocol is provided.

July 2015 - Approximate Patient enrollment begins at Mayo

April 2016 Approximate Data Safety Monitoring Board (DSMB) contact via teleconference or E-mail meeting to meet biannually and/or not less-than once a year.

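### The Sample Size section proposes 75 patients per arm but derives and plans 64; the 75 per arm (150 total) used elsewhere has no derivation or stated power

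*Combined protocol and SAP*

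**What the plan says.** The Sample Size section gives two sizes in one paragraph. It begins "We propose testing 75 patients in each study arm". It then takes the pilot event rates for the composite outcome (7.1% on pentoxifylline, 28.6% on placebo) with a two-sided 5% type I error, and concludes that "58 patients in each group would be needed to achieve 80% power to detect the anticipated difference". To allow for up to 10% dropout it ends with "we plan to enroll 64 patients in each group", which is 128 in total.

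The other sections follow the larger number:

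- The Project Summary has 75 patients in each group, 150 in total.
- The section headed Experimental Design or Project Summary states "The study will have 2 groups of 75 patients each". It attributes the group size to the pilot study, "providing for a dropout rate of 10% during the study", but shows no calculation.
- Feasibility projects that "it would take 24 months at Mayo to recruit 150 patients", and then provides for a 6-month extension if recruitment goals are not met by about that time.

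**The concern.** Both figures are statements of the trial's size in current text, and they cannot be read as different quantities. The 75 cannot be the evaluable number, because that is 58, and it exceeds the 64 to be enrolled. Nor can it reflect a larger dropout allowance: the design section, where 75 appears, cites the pilot and 10% dropout, which is the basis that leads to 64 in the Sample Size section.

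Two things are at stake. First, the only stated power, 80%, belongs to 58 evaluable patients per arm, so a reader cannot tell what power a 150-patient trial was meant to have. Second, the target governs conduct. Data Analysis allows an interim look when accrual is below target, and Feasibility allows an extension if the goal is missed. With 128 to 149 patients enrolled, the trial would have met one stated target and missed the other, and either stopping or continuing could be defended from the text.

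**Working it through.** **Inputs.** From Sample Size: p1 = 0.071, p2 = 0.286, two-sided alpha 0.05, power 80%, dropout 10%. Two equal groups. From Preliminary Results: "Both groups had 14 patients, evenly matched for age and sex", so the rates correspond to 1/14 and 4/14. From Feasibility: about 250 patients a year, 60% directly admitted, 50% consenting.

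**Reproducing 58.** The plan names no formula, so several were tried. With d = 0.286 − 0.071 = 0.215 and mean rate p̄ = 0.1785:

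- Pooled-variance formula: n = [1.960·√(2p̄(1−p̄)) + 0.842·√(p1(1−p1) + p2(1−p2))]² / d² = [1.960·√0.2933 + 0.842·√0.2702]² / 0.0462 = 48.60, so 49.
- With continuity correction: n′ = (n/4)·[1 + √(1 + 4/(n·d))]² = (48.60/4)·[1 + √(1 + 4/10.45)]² = 57.53, so **58**, matching the plan.
- The unpooled and arcsine formulas each give 46. The exact fractions 1/14 and 4/14 give 57.91 with the correction, again 58.

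**From 58 to enrolment.** 58 × 1.10 = 63.8, so 64. 58/0.9 = 64.4, so 65. The stated inputs therefore give 64 to 65 per arm, 128 to 130 in total. Reaching 75 from 58 would need a dropout rate of 1 − 58/75 = 22.7%.

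**Power at each size.** Continuity-corrected power = Φ{[(d − 1/n) − 1.960·√(2p̄(1−p̄)/n)] / √[(p1(1−p1) + p2(1−p2))/n]}. For n = 67 this is Φ{(0.2001 − 0.1297)/0.0635} = Φ(1.109) = 0.866. Patients left after 10% dropout are rounded down to whole patients.

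| Enrolled per arm | Left after 10% dropout | Continuity-corrected power | Fisher's exact power |
|---|---|---|---|
| 64 | 57 (57.6) | 79.6% | 81.8% |
| 65 | 58 (58.5) | 80.4% | 82.7% |
| 75 | 67 (67.5) | 86.6% | 89.0% |

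The continuity-corrected gap is 86.6 − 80.4 = 6.2 to 86.6 − 79.6 = 7.0 points. With the exact pilot fractions, power at 57, 58 and 67 is 79.3%, 80.1% and 86.4%. With no dropout, 64 per arm gives 84.8% (Fisher 87.1%) and 75 per arm gives 90.6% (Fisher 92.2%).

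**Could 75 have another origin?** At 90% power the corrected formula gives 73.57, so 74, with the printed rates, and 74.07, so 75, with the exact fractions. Both are before dropout; adding 10% gives 74/0.9 = 82.2, so 83, or 75/0.9 = 83.3, so 84. Separately, the feasibility rate is 250 × 0.6 × 0.5 = 75 patients a year, or 150 in two years. The plan states neither as its basis, and the first would leave out the dropout allowance that the design section says is included.

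**Time to recruit at 75 a year.** 128 patients take 128/75 × 12 = 20.5 months, 130 take 20.8 and 150 take 24.0.

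**The case against.** The contradiction itself is not in dispute; the case against concerns its weight. Most of the text points to 150, so 64 may be one sentence left unreconciled, and a trial that enrols more than its calculation requires is not harmed in power. Anyone who reads that 58 evaluable patients give 80% can see that 75 gives more. That stands, and it is why the point is not rated higher.

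The 79.6% for 64 enrolled depends on rounding 57.6 down to 57. At 57.6 the same formula gives 80.06%, and Fisher's exact test already exceeds 80% at 57. The plan also describes 10% dropout as an upper limit and unlikely. So choosing 64 or 65 is a one-patient matter and not a separate error.

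The design section does assert a basis for the group size, so it would be wrong to say that none is offered. But the pilot with 10% dropout yields 64 to 65, not 75.

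Finally, the continuity correction is inferred from its agreement with 58, and Data Analysis names tests for secondary endpoints only. Any power written into the plan therefore needs its method confirmed by the sponsor. That affects the wording of the fix, not the need for it.

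**Conclusion.** The concern holds and should be fixed. The plan states 75 and 64 per arm, 150 against 128 in total, with nothing to reconcile them. Its stated inputs support 64 to 65 per arm; the probable target of 150 has neither a derivation nor a stated power. The difference is 20 to 22 patients, about 3.2 to 3.5 months at the projected accrual rate, and about 6 to 7 points of power after 10% dropout.

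The power figures assume the pilot rates of 7.1% and 28.6%, which come from 14 patients per group, the composite outcome in the Sample Size section, a two-sided 5% test and the continuity-corrected formula. On those assumptions neither size is materially underpowered. What is unclear is the target itself, and with it the end of accrual and the meaning of under-accrual for the interim analysis and the extension.

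**What to change.** State one enrolment target with its power, dropout allowance and named method, and use it throughout. Either option works:

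- **Keep 150.** Replace the 64-per-group sentence with, for example: 58 evaluable patients per arm give 80% power (two-sided 5%, continuity-corrected); 75 per arm (150 in total) will be enrolled, leaving 67 per arm after 10% dropout and about 87% power. The sponsor should confirm the method; under Fisher's exact test the last figure is 89%. The Project Summary, design section, Feasibility paragraph and 24-month projection stay as they are. Against the written 64 per group this means 22 more patients and about 3.5 months.
- **Keep 64 per arm (128), or 65 (130)** so that 58 whole patients remain after dropout. Correct 75 and 150 in the Project Summary, the design section, the opening of Sample Size and Feasibility. Against 150 this saves 20 to 22 patients and about 3.2 to 3.5 months, and gives up about 6 to 7 points of power.

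Either way the change to the document is wording only.

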Adverse event management: Most of the side effects observed with long clinical use of pentoxifylline are mild and uncommon. Any unexplained hemorrhage of any magnitude will result in stopping the drug. Any of the serious events listed in the drug package insert and informed consent form will result in stopping of the drug if alternative explanation is not found. Adverse events experienced by subject during the study will be evaluated by the investigator. Adverse events will be documented and reported in the IRB annual continuing review. Serious adverse events will be evaluated by both the investigator and found to be related to study then DSMB will be contacted. Serious adverse events will reported according to the FDA and IRB policies and guidelines.

DSMB

For this safety analysis, the study statistician will prepare a blinded assessment of adverse events and severe adverse events by study group. The DSMB, consisting of clinical experts in GI and AP who are not involved in the study will review the blinded report to assess whether they feel either study group is experiencing more adverse events or severe adverse events or more-severe adverse events or severe adverse events. If the DSMB concludes that one group has greater risk, the study statistician will determine whether that group was randomized to pentoxifylline or placebo; if the pentoxifylline group is at risk, the study team will stop enrolling patients and administering the study drug, but will continue to monitor follow-up in previously enrolled patients. DSMB will be constituted by clinicians having experience in TNF- α blockade therapy.

DSMB will receive general updates as well as having contact meeting not less than once a year (per FDA regulation) with either face-to-face, or telephone conference call or e-mail contact. Face-to-face meetings will be conducted as all member schedules allow. If unable to do face-to-face then telephone conferencing or e-mail will be utilized.

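### The only event-level trigger for contacting the DSMB is a blinded investigator's finding of relatedness, and the unfiltered by-group report that would show a disease-like harm has no date.

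*Combined protocol and SAP*

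**What the plan says.** **Event-level route.** Adverse event management has one sentence on when a single event goes to the DSMB: a serious event is evaluated by the investigator and, if "found to be related to study then DSMB will be contacted". In that sentence words seem to be missing after the word both, and only one assessor is named. The section also sends serious events to the FDA and IRB under their policies, and adverse events to the IRB each year. Neither route is said to feed the DSMB.

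**Who judges.** Under Blinding: "Both subjects and investigators will be blinded to the randomization".

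**By-group report.** Under DSMB, "the study statistician will prepare a blinded assessment of adverse events and severe adverse events by study group". The DSMB then considers whether either group has more events or worse ones. This report carries no relatedness condition. No date, patient count or event count triggers it.

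**Frequency.** The DSMB section says "DSMB will receive general updates as well as having contact meeting not less than once a year". It does not say what the general updates contain or when they are sent, and e-mail counts as contact. The milestones schedule has one DSMB entry, about April 2016, with the board "to meet biannually and/or not less-than once a year". Of these two wordings, yearly contact is the only firm commitment.

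**The concern.** The primary outcome under Sample Size includes ICU admission, persistent organ failure, necrosis and infection, intervention and death. These are complications of the disease, and they are also what a harmful drug effect could look like. An investigator who sees one such case, without knowing the arm, has good reason to attribute it to pancreatitis. Judging events one by one is therefore a poor filter here. The useful evidence is the count in one coded group against the other.

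The protocol's own safety rule rests on that comparison, because the DSMB is asked whether one group is at greater risk. Between reviews, however, the only stated prompt to the DSMB is the relatedness judgement, and nothing fixes when the comparison is made. At stake is how many further patients enrol before an imbalance is looked at.

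**Working it through.** **Inputs.** Feasibility: nearly 250 patients a year, about 60% directly admitted, 50% consenting, 150 patients in 24 months. Experimental Design: two groups of 75. Randomization: treatment for 72 hours. Milestones: enrolment from about July 2015, DSMB entry about April 2016. Sample Size: 28.6% of pilot placebo patients had at least one component of the composite.

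**1. Reproduce the plan's figure.** 250 × 0.60 × 0.50 = 75 patients per year. 150 / 75 = 2 years = 24 months, as stated. Monthly accrual is 75 / 12 = 6.25.

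**2. Enrolment between contacts.** Patients = 6.25 × months. With equal groups, half receive pentoxifylline.

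| Gap | Patients | Share of 150 | On pentoxifylline |
|---|---|---|---|
| 6 months (twice yearly) | 37.5 | 25% | about 19 |
| 9 months (July 2015 to April 2016) | 56.25 | 37.5% | about 28 |
| 12 months (yearly floor) | 75 | 50% | about 37 |

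Sample Size also gives 64 per group, or 128 in all. On that total the shares become 37.5/128 = 29%, 56.25/128 = 44% and 75/128 = 59%. Because a course lasts 72 hours, nearly everyone enrolled in a gap has finished treatment before the next contact.

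**3. What a by-group table could show.** The documents give no serious adverse event rate. As an assumption, I take the 28.6% composite as a stand-in for the control rate, with 40%, 50% or 60% on drug. Extra events = n × (drug rate − 0.286). Power is for Fisher's exact test, two-sided 5%, by enumerating the two binomial counts.

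| Patients per arm | Drug rate | Extra events expected | Power |
|---|---|---|---|
| 19 | 40% | 2.2 | 7% |
| 19 | 50% | 4.1 | 20% |
| 19 | 60% | 6.0 | 41% |
| 37 | 40% | 4.2 | 12% |
| 37 | 50% | 7.9 | 37% |
| 37 | 60% | 11.6 | 71% |

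A DSMB does not need statistical significance to act, so these figures describe how small the tables are. They are not a threshold for action.

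**The case against.** The strongest reply is that the safeguard already exists. The by-group report has no relatedness condition, and it makes the very comparison that would expose a disease-like harm. Lifting the condition on single-event notices would not by itself reveal an imbalance, since events must be tabulated by group. This stands. It means the undated report matters at least as much as the filter, and that changing only the filter would not be enough.

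A reader might infer that the DSMB never hears of events judged unrelated, or that an excess would go unseen for much of the trial. The documents do not support that:

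- The report covers all adverse events.
- General updates also go to the board, although their content is not given.
- Yearly contact is a floor, and biannual contact is mentioned.
- April 2016 is marked approximate and is not called the first contact.
- The 56 and 75 patients count both arms. About 28 and 37 of them would be on drug.
- The trigger sentence is garbled and does not literally say that no other event may be notified.

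It is also fair to say that this is a single-centre trial of at most nine doses, of a drug the protocol describes as long used with mild and uncommon side effects, and that serious events reach the FDA and IRB in any case. Step 3 shows that six-month tables are weak for moderate excesses. These points lower the urgency. They do not explain why the DSMB's one event-level prompt should depend on a judgement that this disease makes unreliable.

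**Conclusion.** The point holds as one of timing. Two features together can delay sight of a harm that resembles pancreatitis: a relatedness condition applied by a blinded investigator, and a by-group report with no date. The delay spans about 37 enrolled patients (about 19 on pentoxifylline) if contact is twice yearly, and 75 (about 37 on pentoxifylline) at the yearly floor.

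These figures assume the planned, even accrual, equal groups, and that the report is made only at DSMB contacts. The rates in step 3 are illustrative. Nothing in the documents shows actual harm. The document is dated January 2017, so some of the planned enrolment period has passed. The wording still governs the remaining enrolment and the possible six-month extension. This is an inexpensive improvement to safety oversight that should be made. It does not mean that the trial lacks oversight.

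**What to change.** 1. In Adverse event management, remove the relatedness condition for DSMB notification and repair the sentence. If a second assessor was intended, name that role. The relatedness assessment can still be recorded.
2. Have the study statistician send the DSMB all deaths and serious adverse events by coded group, whatever their attribution. State whether primary-outcome events are included. The protocol does not say, and the by-group report names severe events but not serious ones.
3. Tie the existing by-group report to a twice-yearly contact, which the milestones already mention. Make the DSMB section and the milestones agree, and state what the general updates contain.

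The statistician already prepares coded reports, so clinical staff stay blinded. No treatment or stopping rule changes. The cost is a protocol wording change, short coded listings and slightly more reading for the DSMB. Early tables will have about 19 patients per arm and would reliably show only large imbalances, so the board should read them as monitoring data and not as tests.

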Patients admitted within 24 hours with AP diagnosis will be included, with the exception of those meeting the exclusion criteria. Those patients that have been identified with AP diagnosis within 72 hours will be approached by the study coordinator and also by the principal investigator (PI) (whenever feasible) to explain the study and obtain written consent.

Inclusion criteria

- Enrollment within 72 hours of diagnosis of AP
- Ability to give informed consent or a legal adult representative LAR able to give informed consent for subject when needed as defined but LAR use guidelines.
- Adult subjects of age ≥ 18 years.

Exclusion Criteria:

- Moderate or severe congestive heart failure,
- History of seizure disorders or demyelinating disease,
- Nursing mothers,
- Pregnancy,
- History of prior tuberculosis or risk factors for tuberculosis
- Evidence of non- corticosteroid immunosuppression (such as malignancy, chronic renal failure, chemotherapy within 60 days, and HIV)
- Evidence of active hemorrhage,
- Paralytic ileus with severe nausea and vomiting.

Laboratory test and assessments:

Test / Procedure	Day 0	Day 1	Day 2	Day 3	Day 4	Day 5
TNF-a*	X	X	X	X	X	X
IL-6*	X	X	X	X	X	X
IL-8*	X	X	X	X	X	X
Pregnancy Test X						
CRP	X*	X*	X*	X*	X*	X*

* Note: The C-RP, TNF-a, IL-6, IL-8 tests are charged to the research study. All other tests listed are clinical standard care for acute pancreatitis.

The pregnancy test may be done as standard of care and will be closely monitored by study staff to assure completion before subject receives study medication.

Follow up process may be done by telephone contact or review of medical records dependant on subjects follow-up information availability. Some subjects may do their follow up visits at a

local facility not return to Mayo Clinic Rochester for follow up visit within the 4 month time frame (plus or minus 15 days). Thus their medical record may not be available in the Mayo Network system. Then a telephone contact may be done to acquire the follow up information.

Randomization:

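### The clinical composite has no common ascertainment window: the only recording rule stated for analysis data ends at discharge, and the 4-month follow-up is tied to no endpoint

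*Combined protocol and SAP*

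**What the plan says.** **Outcome.** The Sample Size section states: "Our primary outcome will be whether the patient develops any of the following outcomes of moderate or severe AP". It lists a stay over 10 days, ICU admission, persistent organ failure, necrosis and infection, SIRS, intervention and death. No assessment period is given. Specific Aims (Aim 1) also names necrosis and infection among the primary endpoints, and death, length of stay, ICU need and intervention as secondary ones.

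**Recording.** Data Collection and Handling says: "The clinical and research laboratory data will be recorded every day until discharge". The next sentence reads: "Early discharges before completion of 3 days of drug or 5 days of study of markers after drug administration is not considered as protocol violation". Its second half sets the rule for these patients, namely that "data until the time of discharge will be recorded for the purpose of analysis".

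**Follow-up.** The text after the laboratory schedule says: "Follow up process may be done by telephone contact or review of medical records dependant on subjects follow-up information availability". The timing is 4 months, plus or minus 15 days. What is collected is not stated, and no endpoint is linked to it.

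**Survival.** Data Analysis plans a Kaplan-Meier estimate without a time origin, horizon or censoring rule.

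**Expected effect on stay.** Aim 1 hypothesises less prolonged hospital stay on the drug. Preliminary Results reports that in the pilot "the pentoxifylline group experienced a 29% reduction in length of hospital stay".

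**The concern.** Discharge happens after randomisation, and treatment is expected to move it. If clinical outcomes are recorded only until discharge, the arm that goes home sooner is watched for less time. A late infection, intervention or death in a patient already at home would go unrecorded, while the same event in a patient still in hospital would be counted. Any resulting bias would favour the drug.

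Analysis by intention to treat does not prevent this. It governs who is analysed, not how long each patient is observed. Events lost equally in both arms would not bias the comparison under the null, but they would lower the event rates and the power.

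The text also leaves room for two teams to score the same patient differently on the outcome that sets the sample size.

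**Working it through.** **1. The passages side by side**

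| Item | What is stated | What is not stated |
|---|---|---|
| Composite | Seven kinds of event | Assessment window |
| Recording for analysis | Until discharge | Whether this covers clinical outcomes or only markers and laboratory data |
| 4-month contact | Timing and method | Data items; endpoint served |
| Survival | Kaplan-Meier | Origin, horizon, censoring |

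No section says that the composite closes at discharge. None says that it runs to 4 months or any other day.

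**2. Who is exposed**

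A patient still in hospital after day 10 is already an event through length of stay, so longer observation cannot change that patient's composite status. Only a patient discharged by day 10 whose first qualifying event comes later can be missed. The separate endpoints of infection, intervention and death lack this protection. For them, the same event on day 12 could be recorded in an inpatient and missed in a patient already at home.

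**3. The plan's own sample size**

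Inputs from the Sample Size section: p1 = 0.071, p2 = 0.286, two-sided 5%, power 80%. Then d = 0.215 and p̄ = 0.1785.

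- Uncorrected: n = [1.96√(2p̄(1−p̄)) + 0.8416√(p1(1−p1) + p2(1−p2))]² / d² = [1.96 × 0.5415 + 0.8416 × 0.5198]² / 0.215² = 48.6.
- With continuity correction: n/4 × [1 + √(1 + 4/(nd))]² = 57.5, so 58 per group, as stated.

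**4. Equal loss in both arms (assumed shares)**

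Power = Φ{[(d − 1/n)√n − 1.96√(2p̄(1−p̄))] / √(p1(1−p1) + p2(1−p2))}, with both rates multiplied by (1 − share lost).

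At n = 75:

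- No loss: (0.215 − 0.0133) × 8.660 = 1.746; (1.746 − 1.061)/0.5198 = 1.318; power 90.6%.
- 20% lost: rates 5.68% and 22.88%, d = 0.172; (1.374 − 0.970)/0.4796 = 0.843; power 80.0%.

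| Events lost in each arm | Rates | Power, 75 per arm | Power, 58 per arm |
|---|---|---|---|
| 0% | 7.1% vs 28.6% | 90.6% | 80.4% |
| 10% | 6.4% vs 25.7% | 86.1% | 74.1% |
| 20% | 5.7% vs 22.9% | 80.0% | 66.8% |
| 30% | 5.0% vs 20.0% | 72.4% | 58.5% |

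**5. Unequal loss with no true effect (assumed shares)**

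True rate 28.6% in both arms, 75 per arm, two-sided 5% test without continuity correction. Rejection = Φ[(d − 1.96·se0)/se1] + Φ[(−d − 1.96·se0)/se1], where d is now the observed difference and se0 and se1 are the pooled and unpooled standard errors.

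| Lost, placebo / drug | Observed, placebo vs drug | Rejection |
|---|---|---|
| equal shares | equal | 5.0% |
| 5% / 15% | 0.286 × 0.95 = 27.2% vs 0.286 × 0.85 = 24.3% | 6.8% |
| 5% / 25% | 27.2% vs 0.286 × 0.75 = 21.5% | 12.9% |

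This shows direction and sensitivity only. No share of events after discharge appears in the documents.

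**The case against.** The strongest reply is that the discharge sentence has a narrow purpose. It sits in a paragraph that opens with assay handling, and it explains that missed doses or marker draws are not protocol violations. The sentence before it can be read as covering laboratory data only. A reader might infer that a patient readmitted after discharge is scored as a non-event, but no section says so. This part of the reply stands. It does not settle the matter, because the early-discharge sentence refers to data without limit and no other section gives a recording period for clinical outcomes.

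A reader might also infer that the 4-month follow-up is unused, or that survival is censored at discharge. The documents support neither. A telephone call is planned where records are unavailable, the DSMB section keeps enrolled patients under follow-up if the drug is stopped, and the contact is a natural source for deaths. The plan is silent here, not contrary.

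The pilot also limits the size for the composite. The reported 29% reduction in stay is said to mean that no drug patient stayed over 10 days. With 14 per arm, it may well be 4/14 against 0/14 long stays. The placebo composite rate is also 4/14 = 28.6%. On that reading every placebo event in the pilot was already a long stay, and none could be lost at discharge. The caveat is that the pilot selected patients with predictors of severe disease, whereas this trial enrols all comers.

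Finally, the unequal-loss scenario is strained. It assumes no effect on a composite that includes long stay and ICU admission, yet earlier discharge on the drug. SIRS, organ failure and first ICU admission probably occur mostly in hospital (an assumption), which narrows the exposure further.

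**Conclusion.** The point holds as a conditional one. The plan fixes no common window for the composite, its one recording rule for analysis data runs to discharge, and it gives the 4-month follow-up no stated role. If the discharge rule is applied to clinical outcomes, ascertainment depends on an event that treatment is expected to bring forward, and it can favour the drug. The documents do not show that the composite is closed at discharge, so this is not a demonstrated bias.

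The size cannot be derived from the documents. At the proposed 75 per arm, an assumed equal loss of up to 20% of events still leaves power at the 80% target; at 58 per arm any such loss takes power below it. No change in sample size follows. The change should be made because the defect touches the powered outcome and is cheap to remove. Confidence is moderate.

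**What to change.** - In Data Collection and Handling, limit the discharge rule to daily marker and laboratory data.
- In Sample Size and Data Analysis, define the composite and each component over one fixed period from randomisation for every patient, regardless of discharge, ending at the planned 4-month contact. Because that contact may fall 15 days either side, name the cut-off day and apply it using event dates.
- Score the stay over 10 days on the index admission.
- State that the 4-month contact collects, with dates, readmission, ICU admission, organ failure, necrosis or infection, intervention and vital status.
- For Kaplan-Meier, state the origin and horizon, and censor at last known vital status.

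The cost is protocol wording and a few more data fields on a contact already planned, with no new visit. The drawback is that some events at outside hospitals will be known only by telephone, and a few patients may be unreachable. Report the number unreachable by arm.
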